6.2.2 Secondary Outcome Measures

- i) **Device usability rating**, measured by the fraction of subjective usability ratings ≥ 4 on the post-test questionnaire. Clinician-reported usability will be scored on a five-point LIKERT scale² ranging from 1 (very hard to use) to 5 (very easy to use). Observations will be made throughout the session.
- ii) **Device usability subjective feedback**, focussing on any clinician-reported concerns regarding set-up, operation and cleaning.
- iii) **Device tolerability ratings**, measured by the fraction of subjective tolerability ratings ≥ 3 on the post-test questionnaire. Participant-reported tolerability will be scored on a four-point LIKERT scale ranging from 1 (very intolerable) to 4 (very tolerable).
- iv) **Device tolerability subjective feedback**, focussing on any participant-reported concerns regarding the comfort of the headgear including how hot their head felt, weight of the headgear, how secure the headgear felt and the impact of the headgear on their performance during the investigation.

6.3 Trial Participants

6.3.1 Overall Description of Trial Participants

Participants will be patients of the Liverpool University Hospitals NHS Foundation Trust with suspected EILO and who have been selected for CLE testing to confirm the diagnosis.

6.3.2 Inclusion Criteria

- Participant is willing and able to give informed consent for participation in the study.
- Male, female or non-binary, aged 18 years or above.
- Able (in the Investigators opinion) and willing to comply with all study requirements.

² The LIKERT scale is a widely used type of psychometric response scale in which responders specify their level of agreement to a statement typically in five points (Preedy & Watson, 2010). Empirical evidence shows this scale has 90% reliability and 89% validity (Louangrath, 2018).

- Able to undergo a CLE test as judged by the clinician, and where a clinical need of the test for the delivery of healthcare has been identified.

6.3.3 Exclusion Criteria

The participant may not enter the study if ANY of the following apply:

- Pain, sore areas, broken skin at the site of contact with the headgear.
- Devices, e.g. cochlear implants, that impede the use of the headgear.
- Head circumference is less than 50cm or greater than 63cm, reflecting the 3rd centile for females and 97th centile for males, respectively (Bushby, 1992).
- Exclusion criteria for endoscopy procedures:
 - Skull base/facial surgery or fracture within the previous six weeks
 - Major or life threatening epistaxis within the previous six weeks
 - Trauma to nasal cavity secondary to surgery or injury within the previous six weeks
 - Sino-nasal and anterior skull base tumours/surgery
 - Nasopharyngeal stenosis
 - Craniofacial anomalies
 - Hereditary haemorrhagic telangiectasia
 - Severe movement disorders and/or severe agitation
 - Vasovagal history
 - Bleeding risks
- Any other exclusion criteria as identified by the current endoscopy procedure.

6.4 Study Procedures

6.4.1 Informed Consent

The participant must personally sign and date the latest approved version of the informed consent form before any study specific procedures are performed.

Written and verbal versions of the participant information and Informed consent will be presented to the participants detailing no less than: the exact nature of the study; the implications and constraints of the protocol; the known side effects and any risks involved in taking part. It will be clearly stated that the participant is free to withdraw from the study at any time for any reason without prejudice to future care, and with no obligation to give the reason for withdrawal. Participants will be assured that their individual results will be used to help diagnose and treat their breathlessness.

The participant will be allowed as much time as wished to consider the information, and the opportunity to question the Investigator, their GP or other independent parties to decide whether they will participate in the study. Written Informed Consent will then be obtained by means of participant dated signature and dated signature of the person who presented and obtained the informed consent. The person who obtained the consent must be suitably qualified and experienced, and have been authorised to do so by the Chief/Principal Investigator. A copy of the signed Informed Consent will be given to the participants. The original signed form will be retained at the study site.

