- Was the endoscopy image clear and stable enough to allow a diagnosis of EILO to be confirmed or ruled out? (Note that participants are withdrawn from the study if the

CLE test is unable to allow a diagnosis of EILO to be confirmed or ruled out due to reasons unrelated to the headgear.)

- How easy was it to use the headgear?

- 1) Very hard to use;
- 2) Hard to use;
- 3) Neither hard nor easy to use;
- 4) Easy to use;
- 5) Very easy to use.

- Please record any concerns about the headgear, thinking particularly about set-up, operation and cleaning.

Data will be handled as detailed in Section 13 Data Handling and Record Keeping.

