6.5 Discontinuation/ Withdrawal of Participants from Study Treatment

Each participant has the right to withdraw study at any time. In addition, the investigator may discontinue a participant from the study at any time if the investigator considers it necessary for any reason including:

- Pregnancy
- Ineligibility (either arising during the study or retrospective having been overlooked at screening)
- Significant protocol deviation
- Significant non-compliance with study requirements
- An adverse event, adverse device effect, serious adverse device effect or unanticipated adverse device effect which results in cessation of the CLE test or inability to continue to comply with study procedures
- Consent withdrawn
- If the participant cannot wear the headgear, e.g. it does not fit.
- If the CLE test is unable to allow a diagnosis of EILO to be confirmed or ruled out due to reasons unrelated to the headgear, e.g. the participant cannot tolerate the endoscopy.

Withdrawn participants will be replaced.

The reason for withdrawal will be recorded in the Case Report Form (CRF).

If the participant is withdrawn due to an adverse event, the investigator will arrange for follow-up visits or telephone calls until the adverse event has resolved or stabilised.

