9.5 Procedure for Accounting for Missing, Unused, and Spurious Data

If the data is missing completely at random, and the fraction of missing data is no larger than 5%, then the missing data will be ignored in the analysis. If the data is missing at random, deletion is not a viable strategy, so imputation procedures will be applied to avoid biased estimates (Harrell, 2015).

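### Replacing participants who withdraw without a reason after the headgear is fitted, with no rule on whether they are analysed, can bias the primary proportion upward

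*Combined protocol and SAP*

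**What the plan says.** Section 6.4.1 allows withdrawal at any time "without prejudice to future care, and with no obligation to give the reason for withdrawal". Section 6.5 repeats the right ("Each participant has the right to withdraw study at any time") and lists grounds for discontinuation. One of them is "Consent withdrawn", with no limit on timing or cause. After the list come two general rules: "Withdrawn participants will be replaced" and "The reason for withdrawal will be recorded in the Case Report Form (CRF").

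Section 6.4.4 sets the order of events. The headgear is fitted at step 2, the endoscope is inserted at step 3 and the test is run at step 5. The clinician then answers whether the image was good enough for a diagnosis. A note there, and a matching ground in 6.5, withdraw the participant when the "CLE test is unable to allow a diagnosis of EILO to be confirmed or ruled out due to reasons unrelated to the headgear".

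Section 9.7 puts all eligible participants in the analysis and does not mention those withdrawn or replaced. Section 9.5 deals with missing data. Its deletion rule reads "the fraction of missing data is no larger than 5%, then the missing data will be ignored in the analysis", and this applies only where the missingness is also completely random. Values that are merely missing at random are imputed. Section 9.1 tests the primary proportion against 49 in 50, and Section 9.3 sets the level at 0.01.

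**The concern.** The note in 6.4.4 implies a sensible principle: a non-diagnostic test leaves the study only when the headgear is not to blame, and otherwise it counts. Applying that principle requires a known cause. A participant who formally withdraws consent with the headgear on, before a diagnostic image is obtained, and gives no reason supplies no cause. The case cannot be placed on either side. Section 6.5 nevertheless sends it down the same route as a case clearly unrelated to the device: withdrawn and replaced.

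The headgear could plausibly contribute to some of these withdrawals. It weighs 1.5 kg (Section 7.1), it is worn during exercise, and the participant questionnaire asks about heat, weight, security and effect on performance. If some unexplained withdrawals are headgear failures and all are replaced, the reported proportion is too favourable. Those participants may also be missing from the tolerability rating. Information not collected when a participant stops may be unrecoverable, so the rule has to exist before data collection.

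**Working it through.** **Inputs.** Planned number 30 (Section 9.2). Reference proportion 49/50 = 0.98, so the reference failure rate is 1 − 0.98 = 0.02 (Section 9.1). Level 0.01, sidedness not stated (Section 9.3). Section 9.2 sets the 30 on practical grounds, so there is no power calculation to reproduce. The plan gives no withdrawal rate; every count or rate of withdrawal below is an assumption.

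**Step 1: where does the unexplained withdrawal go?**
- Section 6.5: withdrawn and replaced.
- Section 6.4.4: the only explicit rule that keeps a participant for analysis covers those given alternative treatment by the clinician. It does not cover withdrawals.
- Section 9.7: could be read as keeping the participant, since eligibility is not lost by withdrawing. The outcome is then the clinician's answer if one is recorded, and missing if not.
- Section 9.5, if missing: one in 31 is 1/31 = 3.2%, under 5%, but the data may be ignored only if also missing completely at random. Two in 32 is 6.25%, over the limit. Imputation is the other route, and no model is given.

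No section requires an answer for such a participant or says how to score the case.

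**Step 2: effect on the estimate and test.** Assume that all 30 completed tests succeed and that h participants withdrew after fitting and were replaced. Under replacement the result is 30/30 = 100% for any h. Counting the h as failures gives 30/(30 + h), with exact p = P(X ≥ h), X binomial with size 30 + h and probability 0.02.

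| h | Proportion | Exact p |
|---|---|---|
| 1 | 30/31 = 96.8% | 1 − 0.98^31 = 0.47 |
| 2 | 30/32 = 93.8% | 0.13 |
| 3 | 30/33 = 90.9% | 0.028 |
| 4 | 30/34 = 88.2% | 0.0046 |

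For h = 4 the probabilities of 0, 1, 2 and 3 failures in 34 are 0.5031, 0.3491, 0.1176 and 0.0256, and 1 minus their sum is 0.0046. The test therefore crosses 0.01 only at four.

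That count assumes no failure among the completed tests. With three visible failures the plan gives 27/30, p = 0.022. One more, from a withdrawal, gives 27/31. The probabilities of 0 to 3 failures in 31 are 0.5346, 0.3382, 0.1035 and 0.0204, so p = 0.0033. What matters is four failures in total.

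**Step 3: effect on the chance of detecting poor performance.** Let q be the true failure rate and w the share of failures that leave as withdrawn and are replaced. The apparent failure rate is q(1 − w)/(1 − qw). For q = 0.10 and w = 0.5 this is 0.05/0.95 = 5.3%, an apparent success rate of 94.7%. With 30 analysed, the exact test at 0.01 needs four or more failures (P = 0.0217 for three or more, 0.0029 for four or more, at a 2% failure rate). The chance of seeing four or more is:

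| Assumed q | w = 0 | w = 0.25 | w = 0.5 |
|---|---|---|---|
| 5% | 6% | 3% | 0.7% |
| 10% | 35% | 20% | 7% |
| 15% | 68% | 47% | 22% |

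**The case against.** The strongest reply is that the gap is narrow. Asking to stop exercising is not the same as withdrawing consent, and nothing in the documents equates them. A participant who stops early but stays in the study is still scored through the clinician's image question, and is removed only if the cause is unrelated to the headgear. Participants also have a clinical need for the test. This stands: the point covers only formal, unexplained withdrawals after fitting and before a diagnostic image.

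Several stronger readings are tempting, and the documents do not support them:
- *The consent wording is the defect.* It is not. The problem is unconditional replacement and an analysis set that is silent about it.
- *Such withdrawals can remove only failures.* Someone may withdraw after a diagnostic image, which removes a success, or because of the endoscope, which 6.5 excludes on purpose. Heat and weight bear mainly on tolerability; discomfort with a clear image is not a primary failure.
- *The failure is lost on every path.* If 9.7 keeps the participant and the clinician answers no, it is counted.
- *The 5% rule would simply drop it.* That rule also requires data missing completely at random, which does not fit a withdrawal caused by the headgear.
- *The event is likely.* If 2% to 10% of fitted participants asked to stop, the chance of at least one in 30 would be 1 − 0.98^30 = 45% to 1 − 0.90^30 = 96%. But those rates are assumed and describe any request to stop. At an equally assumed 0.2% to 0.5% for the narrower event, the chance is 1 − 0.998^30 = 6% to 1 − 0.995^30 = 14%.
- *Crossing 98% is decisive.* With 30 participants any single failure does that (29/30 = 96.7%).

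The participant information sheet and the CRF are not among the documents, so they may already record stop timing or cover retention of data. That would ease collection, but it would not supply the missing analysis rule.

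**Conclusion.** The concern holds in a limited form. Followed as written, Sections 6.5 and 9.7 allow a headgear-related failure to leave the primary proportion as an unexplained, replaced withdrawal, and no rule brings it back. The bias can be upward. Its size depends on a rate the plan does not give. If all 30 completed tests succeed, one case counted as a failure moves the estimate from 100% to 96.8% with no change in the test decision (p = 0.47), and four are needed to reach 0.01. Fewer suffice only if failures are already visible among the completed tests. These figures treat each unexplained withdrawal as a failure, which is the conservative extreme.

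A neighbouring ground in 6.5, "If the participant cannot wear the headgear, e.g. it does not fit", takes out device-related cases more directly. It should be considered when the same sections are revised.

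**What to change.** In Sections 6.5 and 9.7, leaving the consent right unchanged:

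1. Replace without counting only those who withdraw before step 2 of the order of events in 6.4.4 (headgear fitted).
2. For withdrawals at or after step 2, record the timing. Invite, but do not require, a reason and a tolerability rating. Have the clinician answer the image question where consent allows the data to be used.
3. Report the number fitted and the number withdrawn after fitting.
4. Give the primary proportion over all fitted participants, except those with a documented reason unrelated to the headgear. Score a diagnostic image already obtained as success and an unexplained non-diagnostic stop as failure. Do this at least as a prespecified sensitivity analysis beside the completed-test proportion.
5. Report the number of requests for data removal.

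The cost is wording and a timing entry on the CRF if it has none, with no extra participants or visits. The downside is that the all-fitted figure is conservative and may be slightly less favourable, since some unexplained stops will be due to the endoscope and not the headgear. Showing it beside the completed-test figure lets a reader see the range between the two.

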6.4.2 Screening and Eligibility Assessment

The Principal Investigator will review patient records from an existing list of patients awaiting CLE tests. All patients will have been referred for opinion regarding their breathlessness. Participants will be checked for eligibility to enter the study prior to arranging a clinic session. This service is not currently offered by LUHFT.

For all potential study participants, a consultation appointment will be arranged to be conducted at least a week before the investigation appointment. During the consultation, the study will be explained, and the participant will be given the Participant Information Sheet. The screening procedure will be conducted during the consultation appointment. This will involve an eligibility check to ensure that the participant meets the inclusion criteria and none of the exclusion criteria apply, as defined in Sections 6.3.2 and 6.3.3, respectively.

6.4.3 Baseline Assessments

Head circumference, recorded during the investigation appointment.

6.4.4 Subsequent assessments

Following the consultation appointment, the participant will attend one investigation appointment to undergo the CLE test on-site at the Outpatient Department, Alexandra Wing, Broadgreen Hospital. There will be no follow-up assessments.

On the day of the investigation appointment, the Principal Investigator will address any questions or concerns before the investigation begins. If the participant still wishes to partake in the study, signed consent will be obtained from the participant. The right of the participant to refuse to participate without giving reasons will be respected. After the participant has entered the study the clinician remains free to give alternative treatment to that specified in the protocol at any stage if he/she feels it is in the participant's best interest, but the reasons

for doing so should be recorded. In these cases, the participants remain within the study for the purposes of data analysis.

Eligibility will be reviewed for any changes, ensuring that the participant meets the inclusion criteria and none of the exclusion criteria apply. As part of this, the circumference of the participant's head around the forehead will be measured and recorded. Signed consent will then be obtained. The participant will then undergo the CLE test following standard clinical practice.

The order of events of the aspects of the investigation related to the headgear will be:

1. The headgear is prepared for use.
2. The headgear is fitted onto the participant's head.
3. The endoscope is inserted into the participant.
4. The endoscope is fitted onto the headgear.
5. The CLE test is carried out.
6. The endoscope is removed from the headgear.
7. The endoscope is removed from the participant.
8. The headgear is removed from the participant.
9. The headgear is cleaned and stored.

Following completion of the CLE test, the participant will complete a questionnaire:

- How tolerable was the headgear during the investigation?
 - 1) Highly intolerable
 - 2) Intolerable
 - 3) Tolerable
 - 4) Highly tolerable
- Please tell us any concerns about the headgear, thinking about how comfortable it was, how hot your head felt, the weight of the headgear, how secure it felt and the impact of the headgear on your performance during the investigation.

Following the appointment, the clinician will complete a questionnaire including:

- Was the endoscopy image clear and stable enough to allow a diagnosis of EILO to be confirmed or ruled out? (Note that participants are withdrawn from the study if the

CLE test is unable to allow a diagnosis of EILO to be confirmed or ruled out due to reasons unrelated to the headgear.)

- How easy was it to use the headgear?

- 1) Very hard to use;
- 2) Hard to use;
- 3) Neither hard nor easy to use;
- 4) Easy to use;
- 5) Very easy to use.

- Please record any concerns about the headgear, thinking particularly about set-up, operation and cleaning.

Data will be handled as detailed in Section 13 Data Handling and Record Keeping.

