2. SYNOPSIS

Study Title	Safe and Effective Headgear Accessory for Exercise-Induced Laryngeal Obstruction Studies (HALOS) – a Device Development Study.
Internal ref. no.	SP0707
Type of study	Interventional
Trial Design	Single Group Assignment.
Trial Participants	Adults with suspected Exercise-Induced Laryngeal Obstruction (EILO) capable of undertaking a Continuous Laryngoscopy during Exercise (CLE) test.
Planned Sample Size	30 participants.
Follow-up duration	There will be no follow-up.
Planned Trial Period	12 months.
Primary Objective	Ensure the HALOS headgear is suitable for facilitating CLE tests.
Secondary Objectives	
 • Validate risk scores identified in risk management documentation. • Validate mitigations of hazards identified in risk management documentation. • Uncover previously unforeseen hazards, especially any related to usability.
Primary Endpoint	Device effectiveness , measured by the proportion of CLE tests where the endoscopy image was clear and stable enough to allow a diagnosis of EILO to be confirmed or ruled out.
Secondary Endpoints	
i) Device usability rating, measured by the fraction of subjective usability ratings ≥ 4 on the post-test questionnaire. Clinician-reported usability will be scored on a five-point LIKERT scale¹ ranging from 1 (very hard to use) to 5 (very easy to use). Observations will be made throughout the session.
 
ii) Device usability subjective feedback, focussing on any clinician-reported concerns regarding set-up, operation and cleaning.
 
iii) Device tolerability ratings, measured by the fraction of subjective tolerability ratings ≥ 3 on the post-test questionnaire. Participant-reported tolerability will be scored on a four-point LIKERT scale ranging from 1 (very intolerable) to 4 (very tolerable).
 
iv) Device tolerability subjective feedback, focussing on any participant-reported concerns regarding the comfort of the headgear including how hot their head felt, weight of the headgear, how secure the headgear felt and the impact of the headgear on their performance during the investigation.

Device Name	Headgear Accessory for Laryngeal Obstruction Studies (HALOS)

¹ The LIKERT scale is a widely used type of psychometric response scale in which responders specify their level of agreement to a statement typically in five points (Preedy & Watson, 2010). Empirical evidence shows this scale has 90% reliability and 89% validity (Louangrath, 2018).

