5.2 Secondary Objectives

Validate risk scores identified in risk management documentation.

Validate mitigations of hazards identified in risk management documentation.

Uncover previously unforeseen hazards, especially any related to usability.

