6. TRIAL DESIGN

6.1 Summary of Trial Design

The study is an interventional clinical trial involving a single group of 30 participants undergoing a CLE test with the HALOS headgear.

Participants will be required to attend a single consultation and screening appointment to discuss the investigation procedure, and this will occur at least a week before the CLE test. Participants will then attend one appointment for the CLE test. There will be no follow up assessments using the headgear.

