8.2 Reporting of AEs

All AEs occurring during the study observed by the investigator or reported by the participant, whether or not attributed to the device under investigation, will be reported, without undue delay, to the Chief Investigator and LUHFT R&D and recorded on the hospital incident reporting system, in the source data (medical notes) and the CRF. Any questions concerning adverse event reporting should be directed to the Chief Investigator in the first instance.

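### No contact after the test day, no adverse event window and no direct injury question: delayed or unvolunteered device effects rest on spontaneous reports, which weakens the hazard objectives

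*Combined protocol and SAP*

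**What the plan says.** **Follow-up.** The Synopsis says "There will be no follow-up". Section 6.1 is narrower: "There will be no follow up assessments using the headgear". Section 6.4.4 says "There will be no follow-up assessments".

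**Last scheduled data.** In 6.4.4, "Following completion of the CLE test, the participant will complete a questionnaire". It has one four-category tolerability rating, about the test itself, and one open item inviting concerns, with prompts on comfort, heat, weight, security and performance. The clinician's form follows the appointment. Its listed items are image adequacy, ease of use, and an open item on concerns that points to set-up, operation and cleaning. Section 6.2.2 adds that observations are made during the session.

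**Safety capture.** Section 8.2 covers "All AEs occurring during the study observed by the investigator or reported by the participant", whether or not attributed to the device. It gives no start or end date for each participant. Section 15 places the end of the study after the last data collection and the analysis. Section 8.3 follows reported events to resolution. Section 6.5 adds: "If the participant is withdrawn due to an adverse event, the investigator will arrange for follow-up visits or telephone calls".

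**What the data are for.** Section 5.2 sets out to validate the risk scores, to validate the mitigations, and to "Uncover previously unforeseen hazards, especially any related to usability". The hypothesis in 4.4 includes that the risks are understood well enough for a benefit/risk evaluation. Under section 16 the results update the device's Risk Log.

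**The concern.** The headgear is a modified safety helmet weighing 1.5 kg, with a steel clamp mount and a steel counterweight (7.1). It holds an endoscope in place while the participant exercises. The plan treats the contact site as relevant, because 6.3.3 excludes anyone with "Pain, sore areas, broken skin at the site of contact with the headgear". The human testing described in 9.2 was done without the endoscope inserted, so this study has to supply the evidence on headgear and inserted endoscope together.

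A participant who finishes the test, hands in the form and notices a problem later is never asked about it. The follow-up in 6.5 and 8.3 starts only once an event is known. The same weakness applies on the day to an effect that the participant does not think to mention, since no item asks about injury and the nine-step sequence lists no contact-site check at removal.

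At stake is how a clean safety record may be read. If few or no device effects are recorded, the clinical evaluation and Risk Log could treat that as support for the existing scores, when it may partly reflect that nobody asked. The early-ending rules in 9.4 and 15 also act only on events that become known.

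**Working it through.** **Step 1. Match each capture route to the kind of effect it can find.**

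| Route | Section | Effect seen on the day | New effect after the visit |
|---|---|---|---|
| Observation during the session | 6.2.2 | Yes, if visible | No |
| Participant form, open item | 6.4.4 | Yes, if volunteered | No |
| Clinician form, open item | 6.4.4 | Yes, if noticed | No contact planned to reveal it |
| Follow-up after withdrawal for an adverse event | 6.5 | Known events only | Known events only |
| Follow-up of reported events | 8.3 | Known events only | Known events only |
| Adverse event reporting | 8.2 | Yes | Yes, if the participant reports it unprompted |

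For a new effect after the visit, only the last row can work, and it has no prompt and no stated window.

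**Step 2. Is there a figure to reproduce?** No. The documents give no hazard rate, reporting rate or safety precision. The 30 participants were set by expected recruitment (9.2). What follows is illustration.

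**Step 3. Chance of recording at least one case.** Inputs: n = 30 (Synopsis, 6.1, 9.2); p, the true rate per participant of a delayed effect (assumed); c, the share of affected participants whose effect reaches the record (assumed). With independent participants,

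P(at least one recorded) = 1 − (1 − p × c)^30.

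| Capture share c | p = 5% | p = 10% |
|---|---|---|
| 1 | 1 − 0.95^30 = 78.5% | 1 − 0.90^30 = 95.8% |
| 0.5 | 1 − 0.975^30 = 53.2% | 1 − 0.95^30 = 78.5% |
| 0.25 | 1 − 0.9875^30 = 31.4% | 1 − 0.975^30 = 53.2% |
| 0.1 | 1 − 0.995^30 = 14.0% | 1 − 0.99^30 = 26.0% |

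**Step 4. What zero recorded events would exclude.** The exact one-sided 95% upper bound on the recorded rate p × c, given 0 of 30, is 1 − 0.05^(1/30) = 9.5%. Dividing by c gives the bound on the true rate:

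- c = 1: 9.5%
- c = 0.5: 0.0950 / 0.5 = 19.0%
- c = 0.25: 0.0950 / 0.25 = 38.0%

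**Step 5. What a scheduled contact could give.** Some people will not respond, so c = 1 is a ceiling. With three quarters captured, the chance at p = 5% is 1 − 0.9625^30 = 68.2%, and the bound after zero events is 0.0950 / 0.75 = 12.7%. The main gain is that the share reached becomes known and can be reported. Under spontaneous reporting c is unknown, so no bound can be stated.

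**The case against.** The case for leaving the plan alone has real substance.

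- **Late reports are allowed.** Section 8.2 runs for the whole study and 8.3 follows what is reported. A reader might infer from the no-follow-up statements that observation stops at the questionnaire and later hazards are missed by design. The documents do not support that: late effects are captured passively.
- **The day itself is better covered than it may look.** Both forms invite any concerns, the clinician's listed items need not be exhaustive, and the session is observed. Usability hazards, which the third objective stresses, arise around set-up, operation and cleaning, and these are asked about.
- **No delayed harm is shown to be expected.** The device is described as Class I and low-risk (9.2), it is worn for one test, and 8.1.2 identifies no potential adverse events. The exclusion in 6.3.3 concerns skin problems already present and says nothing about delayed injury.
- **Relevant papers are not available.** The risk documentation and the participant information sheet are not in the documents. Whether any delayed harm is scored, or participants are told to report later symptoms, cannot be judged.
- **Other routes exist.** The quality system includes post-market surveillance (4.5).

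All of this limits the strength of the point, but none of it supplies systematic capture. That no adverse events are foreseen is not an answer to an objective that looks for unforeseen ones. Post-market surveillance may find hazards later, but it does not make this study's own record more complete.

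**Conclusion.** The gap is one of ascertainment. No contact is scheduled after the test day, no adverse event period is set for each participant, and neither form asks directly about injury. Delayed or unvolunteered effects therefore enter the record only as spontaneous reports under 8.2. For such effects, silence cannot validate a risk score or show that no unforeseen hazard exists.

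The size depends on two unknowns, the true rate and the capture share. At a 5% rate the chance of recording any case runs from 79% with full capture down to 14% with a tenth. Zero events would exclude true rates above 9.5% with full capture, but only those above 38.0% with a quarter. No single row should be taken as a forecast.

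A reader might also infer that a record free of device effects would come about mainly because nobody looked. That goes too far: such effects may truly be rare, and the documents cannot settle it. The primary endpoint and its analysis are unaffected.

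**What to change.** 1. **6.4.4 and the CRF:** add a yes/no contact-site check at headgear removal (step 8 of the listed sequence).
2. **6.4.4:** add one scripted telephone or text contact by the existing team a few days after the test, with the exact timing for the sponsor to set. Ask about new symptoms and record any as adverse events under 8.2.
3. **8.2:** state that each participant's adverse event period runs to that contact.
4. **Synopsis, 6.1 and 6.4.4:** align the three statements on follow-up with each other and with the new contact.
5. **Reporting:** give the number of participants reached alongside the number of events, so that a count of zero can be interpreted.

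If the sponsor declines the contact, limit the hazard objectives in 5.2, and the conclusions carried into the Risk Log, to effects seen during the session.

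The cost is a protocol and CRF amendment and about 30 short calls or messages, with some non-response. No extra visit or staff is needed, and the sample size and primary endpoint stay as they are.
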